Study information

Title	Description of Relugolix Use in Patients with Prostate Cancer: An Analysis of National Veterans Affairs Health Care Network Data
Protocol number	C4751009
Protocol version identifier	Version 1.0
Date	06 May 2024
Active substance	Relugolix (ATC code: L02BX04)
Medicinal product	Orgovyx
Research question and objectives	
This study aims to achieve the following objectives:
 
• Primary objective:
1. To describe demographics and clinical characteristics of patients with prostate cancer (PC) who initiated relugolix• Exploratory objectives:
2. To assess treatment patterns among patients with PC who initiated relugolix3. To estimate adherence and persistence with relugolix among patients with PC who initiated relugolix4. To assess testosterone suppression and prostate-specific antigen responses among androgen deprivation therapy (ADT) naïve patients with PC who initiated relugolix5. To describe and compare demographics and clinical characteristics between Black and non-Hispanic White patients with PC who initiated relugolix6. To describe and compare time to treatment changes between Black and non-Hispanic White patients with PC who initiated relugolix7. To estimate and compare adherence and persistence with relugolix between Black and non-Hispanic White patients with PC who initiated relugolix

Author	PPD PPD	PharmD MS	
--------	------------	-----------	--

This document contains confidential information belonging to Pfizer. Except as otherwise agreed to in writing, by accepting or reviewing this document, you agree to hold this information in confidence and not copy or disclose it to others (except where required by applicable law) or use it for unauthorized purposes. In the event of any actual or suspected breach of this obligation, Pfizer must be promptly notified.

2. LIST OF ABBREVIATIONS

Abbreviation	Definition
ACS	American Cancer Society
ADT	Androgen Deprivation Therapy
ARPI	Androgen Receptor Pathway Inhibitor
ATC	Anatomical Therapeutic Chemical
CA	California
CCI	Charlson Comorbidity Index
CDC	Centers for Disease Control and Prevention
CDW	Corporate Data Warehouse
CIRCL	Center for Integrated Research in Cancer and Lifestyle
CPT	Current Procedural Terminology
dL	Deciliter
DOI	Digital Object Identifier
FDA	Food and Drug Administration
GnRH	Gonadotropin-Releasing Hormone
GPI	Generic Product Identifier
HCPCS	Healthcare Common Procedure Coding System
ICD	International Classification of Diseases
ICD-9-CM	International Classification of Diseases, 9 th Revision, Clinical Modification
ICD-10-CM	International Classification of Diseases, 10 th Revision, Clinical Modification
ICD-10-PCS	International Classification of Diseases, 10 th Revision, Procedures
IEC	Independent Ethics Committee
IRB	Institutional Review Board
LHRH	Luteinizing Hormone-releasing Hormone

MA	Massachusetts
MPR	Medication Processing Ratio
NAACCR	North American Association of Central Cancer Registries
NC	North Carolina
NCCN	National Comprehensive Cancer Network
NCI	National Cancer Institute
ng	Nanogram
NHT	Novel Hormonal Therapy
NJ	New Jersey
NSAA	Non-Steroidal Anti-Androgen
NY	New York
NYC	New York City
PASS	Post-Authorization Safety Study
PC	Prostate Cancer
PDC	Proportion of Days Covered
PH	Proportional Hazards
PMCID	PubMed Central Identifier
PMID	PubMed Identifier
PSA	Prostate-Specific Antigen
SMD	Standardized Mean Difference
SMPA	Sumitomo Pharma America, Inc
US	United States
VA	Veterans Affairs

4. ABSTRACT

Title: Description of Relugolix Use in Patients with Prostate Cancer: An Analysis of National Veterans Affairs Health Care Network Data

Version: 1.0

Date of Protocol: 6 May 2024

Author: PPD

Rationale and Background: Prostate cancer (PC) is the most common cancer and the second leading cause of cancer death among men in the United States. Androgen deprivation therapy (ADT) such as injectable luteinizing hormone-releasing hormone (LHRH) agonists (e.g., leuprolide) is the standard of care for PC patients. ADT treatment can suppress testosterone level to castrate level and delay the progression of the disease. However, LHRH agonist can cause an initial surge of testosterone which results in a flare of symptoms including bone pain or obstructive urinary symptoms. In addition, LHRH agonist can increase the risk of cardiovascular events. As an alternative to LHRH, gonadotropin-releasing hormone (GnRH) antagonist can be considered. Relugolix is a recently approved oral GnRH antagonist, which can rapidly suppress testosterone level without the initial surge. The phase 3 HERO trial of relugolix in advanced PC patients has compared the efficacy and safety of oral relugolix with leuprolide and found that relugolix can achieve castration quicker and can better maintain castration than leuprolide. In addition, the incidence of major adverse cardiovascular events in the HERO trial was lower for relugolix than leuprolide (2.9% vs. 6.2%). Additionally, treatment was associated with a more rapid time to testosterone recovery. The positive results have led to the Food and Drug Administration (FDA) approval of relugolix in December 2020 for the treatment of adults with advanced PC. Currently, relugolix is the only ADT option available in oral form, distinguishing from the traditional injectable LHRH agonists. There are several studies in other diseases have shown that patients have a preference for oral medications due to cultural considerations, apprehension towards injections and needles, and concerns regarding incorrect administration. While the introduction of relugolix has offered a unique opportunity for patients with PC, it's vital to understand how it is being used in real-world. However, few studies have investigated this aspect.

Objectives: This study aims to achieve the following objectives:

- Primary Objective:
 1. To describe demographics and clinical characteristics of patients with PC who initiated relugolix
- Exploratory objectives:
 2. To assess treatment patterns among patients with PC who initiated relugolix
 3. To estimate adherence and persistence with relugolix among patients with PC who initiated relugolix
 4. To assess testosterone suppression and prostate-specific antigen (PSA) responses among ADT naïve patients with PC who initiated relugolix
 5. To describe and compare demographics and clinical characteristics between Black and non-Hispanic White patients with PC who initiated relugolix
 6. To describe and compare time to treatment changes between Black and non-Hispanic White patients with PC who initiated relugolix
 7. To estimate and compare adherence and persistence with relugolix between Black and non-Hispanic White patients with PC who initiated relugolix

Study Design: The current study will be a retrospective data analysis to describe patient characteristics, treatment patterns, adherence, and persistence among patients with PC who initiated relugolix. Adult (aged ≥ 18 years) male patients with PC who had relugolix (initiation date as the index date) will be selected from the National Veterans Affairs (VA) Health Care Network databases. Patients will be required to have continuous eligibility for at least 365 days prior to the index date and 90 days after the index date (unless died within 90 days). The baseline period will be the 365 days prior to the index date. The follow-up period will be from the index date to the earliest of death, end of continuous eligibility or end of data availability.

Population: The overall population will include PC patients who initiated relugolix. The following sample selection criteria will be used:

- Inclusion criteria:
 - Male with ≥ 1 diagnosis for PC
 - Had ≥ 2 prescriptions of relugolix on or after the first observed PC diagnosis. The identification period for relugolix use will be from December 18, 2020 to December 31, 2023
 - Index date: the initiation date of relugolix
 - At least 18 years old at the index date
 - Had continuous activity in the data for at least 365 days before the index date and 90 days following the index date (unless died within 90 days)
- Exclusion criteria:
 - Had surgical castration (bilateral orchiectomy) any time before the index date
 - Participated in clinical trials within 30 days prior to or 90 days after the index date
 - Had any other primary cancer (excluding non-melanoma skin cancer) during the baseline period

Variables: Baseline demographics and clinical characteristics will include variables such as age, race/ethnicity, geographic regions, index year, previous treatment, Charlson Comorbidity Index score, and baseline comorbidities. Outcomes will include treatment patterns, adherence, and persistence with relugolix, and testosterone and PSA responses (if sample sizes allow).

Data Sources: January 1, 2006 to December 31, 2023 data from the National VA Health Care Network will be used.

Study Size: All eligible patients available for the analysis will be included.

Data Analysis: Descriptive analysis will be conducted for baseline demographics and clinical characteristics, and adherence/persistence to relugolix. Means, standard deviations, medians, and interquartile range will be estimated for continuous variables. Counts and percentages will be estimated for categorical variables. Treatment sequence will be described using a Sankey diagram. Kaplan-Meier analysis will be used to describe time to treatment changes. Adherence to relugolix will be calculated using medication processing ratio (MPR) and proportion of days covered (PDC). Persistence with relugolix will be analyzed using Kaplan-Meier analysis. If sample sizes are adequate, the counts and percentages of patients who had testosterone and PSA responses will be summarized. Unadjusted and adjusted comparisons of adherence/persistence to relugolix and time to treatment changes between Black and non-Hispanic White patients will be conducted using appropriate statistical models.

5. AMENDMENTS AND UPDATES

None.

6. MILESTONES

Milestone	Planned date
Approval of the National Veterans Affairs (VA) Health Care Network data application	November 30, 2023
Finalize Protocol	May 06, 2024
Final study report	May 31, 2025

7. RATIONALE AND BACKGROUND

Prostate cancer (PC) is the most common cancer and the second leading cause of cancer death among men in the United States.¹ The National Cancer Institute (NCI) estimated 299,010 new cases and 35,250 deaths of PC in 2024.² While the long-term outlook is positive for early-stage PC, survival rates drastically decrease once the disease has spread beyond the prostate gland (i.e., becoming metastatic) or when the disease becomes castration-resistant.²

Androgen deprivation therapy (ADT) is the standard of care for patients with PC, including such as injectable luteinizing hormone-releasing hormone (LHRH) agonists (e.g., leuprolide) and gonadotropin-releasing hormone (GnRH) antagonist. ADT treatment can suppress testosterone level to castrate level and delay the progression of the disease. LHRH agonist use can cause an initial surge of testosterone which results in a flare of symptoms including bone pain or obstructive urinary symptoms. In addition, LHRH agonist is associated with an increased risk of cardiovascular events.³ As an alternative to LHRH, GnRH antagonist can be considered, which does not cause the initial surge in testosterone level.

Relugolix is a recently approved GnRH antagonist, which can rapidly suppress testosterone level without the initial surge. The phase 3 HERO trial of relugolix in advanced PC patients has compared the efficacy and safety of oral relugolix with leuprolide and has found that relugolix can achieve castration quicker and can better maintain castration than leuprolide.⁴ In addition, the incidence of major adverse cardiovascular events in the HERO trial was also lower for relugolix than leuprolide (2.9% vs. 6.2%).⁴ The positive results have led to the Food and Drug Administration (FDA) approval of relugolix in December 2020.⁵

Relugolix is the only ADT option available in oral form, distinguishing from the traditional injectable LHRH agonists.⁶ While many factors could influence patients' treatment preferences, a

¹ American Cancer Society (ACS), the Centers for Disease Control and Prevention (CDC), the North American Association of Central Cancer Registries (NAACCR), and the NCI. Annual Report to the Nation 2022. https://seer.cancer.gov/report_to_nation. Accessed on May 1, 2023.

² NCI. Cancer Stat Facts: Prostate Cancer. <https://seer.cancer.gov/statfacts/html/prost.html>. Accessed on May 1, 2023.

8. RESEARCH QUESTION AND OBJECTIVES

Using data from the National VA Health Care Network databases, the study will retrospectively analyze data to describe patient characteristics and the treatment patterns of relugolix among patients with PC who initiated relugolix.

Table 1. Objectives and endpoints

Objectives	Endpoints
1. (Primary) To describe demographics and clinical characteristics of patients with PC who initiated relugolix	
Patient baseline demographics and clinical characteristics
2. (Exploratory) To assess treatment patterns among patients with PC who initiated relugolix	
Index treatment regimen distributionTreatment sequence presented by Sankey diagramTime to treatment changes by Kaplan-Meier analysis
3. (Exploratory) To estimate adherence and persistence with relugolix among patients with PC who initiated relugolix	
Adherence to relugolix defined by medication processing ratio (MPR)Adherence to relugolix defined by proportion of days covered (PDC)Persistence with relugolix by Kaplan-Meier analysis
4. (Exploratory) To assess testosterone suppression and prostate-specific antigen (PSA) responses among ADT naïve patients with PC who initiated relugolix	
Testosterone suppressionPSA response
5. (Exploratory) To describe and compare demographics and clinical characteristics between Black and non-Hispanic White patients with PC who initiated relugolix	
Patient baseline demographics and clinical characteristics by race
6. (Exploratory) To describe and compare time to treatment changes between Black and non-Hispanic White patients with PC who initiated relugolix	
Time to treatment changes by Kaplan-Meier analysis by race
7. (Exploratory) To estimate and compare adherence and persistence with relugolix between Black and non-Hispanic White patients with PC who initiated relugolix	
Adherence to relugolix defined by MPR by raceAdherence to relugolix defined by PDC by racePersistence with relugolix by Kaplan-Meier analysis by race

PFIZER CONFIDENTIAL

CT24-WI-GL02-RF02 5.0 Non-Interventional Study Protocol Template For Secondary Data Collection Study 01-
Aug-2023
Page 16 of 41

9. RESEARCH METHODS

9.1. Study design

This is a retrospective, observational study using January 1, 2006 – December 31, 2023 data from the National VA Health Care Network databases. PC patients who initiated relugolix will be selected based on diagnosis codes, age, treatment received, and continuous activity in the health care network. The identification period for relugolix use will be from December 18, 2020 to December 31, 2023. December 18, 2020 is the approval date for relugolix in the US, and December 31, 2023 is the end of available data. The index date will be defined as the initiation date of relugolix. The baseline period will be 365 days prior to the index date (hence the start of the study period is December 18, 2019). The follow-up period will be from the index date to the earliest of death, end of continuous eligibility or end of data availability. Most of the patient characteristics will be described during the baseline period. Certain patient characteristics will be described using all data available prior to the index date (i.e., data prior to December 18, 2019 will also be used if available; see more details in Table 2). Treatment patterns, adherence, and persistence with relugolix, and PSA and testosterone responses (if sample size allows) will be assessed during the follow-up period.

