9.2.1. Inclusion criteria

Patients who met all of the following sample selection criteria will be included:

- Male with ≥ 1 diagnosis of PC (International Classification of Diseases, 10th Revision, Clinical Modification [ICD-10-CM] C61)
- Had ≥ 2 prescriptions of relugolix on or after the first observed PC diagnosis. The initiation date of relugolix will be selected as the **index date**
- At least ≥ 18 years old as of the index date
- Had continuous activity in the data for ≥ 365 days prior to the index date and ≥ 90 days since the index date (unless died within 90 days). The **baseline period** will be defined as the 365-day period prior to the index date. The **follow-up period** will be from the index date to the end of continuous eligibility, data availability, or death, whichever happened first

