	divided by a pre-determined period following treatment initiation (e.g., 6 and 12 months) Adherence will be described as a continuous variable and as a binary variable (<0.80: non-adherent, ≥ 0.80 : adherent)
Treatment persistence	Persistence to relugolix will be described as the proportion of patients who did not discontinue relugolix (i.e., with a treatment gap, switch to another ADT, or death; the minimum days of treatment gap, e.g., 45 or 60 days, will be finalized based on sample size and clinical input) during the follow-up period. Treatment gaps will be assessed from the end of the days of supply of the previous prescription to the earliest of the next prescription or the end of data availability.
PSA response	Only if sample size is sufficient and among patients with at least one baseline and one follow-up period PSA measure: 
• The number and percentage of patients with $\geq 50\%$ and $\geq 90\%$ decline from the baseline PSA to any PSA measurement during the follow-up period and while on relugolix• The number and percentage of patients with the nadir PSA value during the follow-up period and on treatment of relugolix < 0.01, 0.1, and 0.2 ng/mL
Testosterone response	Only if sample size is sufficient and among patients with at least one follow-up period testosterone measure: 
• The number and percentage of patients with at least one testosterone value of <50ng/dL and <20 ng/dL during the follow-up period and while on relugolix 
If sample size is sufficient, the analysis above may be conducted among patients with at least one baseline and one follow-up period testosterone measure

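### With identification and data both ending on 31 December 2023, men starting relugolix after 2 October 2023 can enter only if they die; the bias is one-way but probably small

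*Combined protocol and SAP*

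**What the plan says.** - **Identification window (section 9.1):** "The identification period for relugolix use will be from December 18, 2020 to December 31, 2023". The abstract gives the same dates, attached to the two-prescription criterion.
- **Data end (section 9.1):** "December 31, 2023 is the end of available data".
- **Index date (section 9.1):** "The index date will be defined as the initiation date of relugolix".
- **Minimum follow-up (section 9.2.1):** continuous activity for "≥ 90 days since the index date (unless died within 90 days"). The abstract has the same rule: "continuous eligibility for at least 365 days prior to the index date and 90 days after the index date (unless died within 90 days").
- **Prescriptions (section 9.2.1):** "Had ≥ 2 prescriptions of relugolix on or after the first observed PC diagnosis".
- **End of follow-up (section 9.1):** "The follow-up period will be from the index date to the earliest of death, end of continuous eligibility or end of data availability".
- **Persistence (Table 3, section 9.3):** discontinuation is defined as "with a treatment gap, switch to another ADT, or death".

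No visible text sets a last index date earlier than the end of data, and no exception covers a man whose 90 days are cut short by data end. Section 9.9 discloses the selection caused by requiring two prescriptions, but not this one.

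**The concern.** Waiving a follow-up minimum for early deaths is sound when every entrant could have been followed for the full 90 days: it keeps early deaths in the cohort beside the survivors from the same dates. Once fewer than 90 days of data remain, the same waiver works the other way. Survivors fail the criterion and decedents pass it, so eligibility is decided by an outcome observed after the index date.

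Without the waiver, the late closing date would be harmless, because nobody could enter from the last stretch. With it, that stretch contributes deaths only. Each is an early event in the persistence curve (Objective 3) and in the Cox comparison of persistence by race (Objective 7). The same men are counted in the primary baseline table and in its 2023 index-year category.

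**Working it through.** The plan has no sample size or other figure to reproduce here. The check is calendar arithmetic, followed by an illustration of size.

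**Dates (from section 9.1 and section 9.2.1)**
- Window: 18 to 31 December 2020 is 14 days, plus three years of 365 days: 14 + 1,095 = 1,109 days.
- Last index date with 90 days of data: 31 December 2023 − 90 days = 2 October 2023.
- Affected index dates: 3 October to 31 December = 29 + 30 + 31 = 90 days, or 90 / 1,109 = 8.1% of the window. Valid index days: 1,109 − 90 = 1,019.
- If the index day counts as day 1, the last valid date is 3 October and 89 days are affected.

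**Who can enter from the affected dates**
- Alive at data end: fewer than 90 days of activity and no exception, so excluded.
- Two prescriptions and dead by 31 December 2023: death is necessarily within 90 days, so included.

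**Size (assumptions, not in the documents)**

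Uptake is flat or rises linearly from zero. 90-day mortality is m = 1%, 3% or 5%, with deaths spread evenly over days 0–90. The second prescription comes at once or at day 30; in the latter case only deaths after day 30 can enter.

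*Share of all starts on the affected dates.* Flat: 8.1%. Linear: 1 − (1,019/1,109)² = 15.6%. Nearly all of these starts (97.5% to 99.8%) are excluded, so these shares do not measure the bias.

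*Extra early deaths relative to those from the 1,019 valid days.* A man with d days of data left has a fraction d/90 of his death window observed.
- Flat, deaths from day 0: Σ d/90 for d = 0 to 89 is 4,005/90 = 44.5; 44.5/1,019 = 4.4%.
- Linear, deaths from day 0: Σ (1,108.5 − d)·d/90 = (1,108.5 × 4,005 − 238,965)/90 = 46,673; divided by 1,019²/2 = 519,180.5, this is 9.0%.
- Flat, deaths from day 30: Σ k/60 for k = 1 to 59 is 1,770/60 = 29.5; 29.5/1,019 = 2.9%.
- Linear, deaths from day 30: (1,078.5 × 1,770 − 70,210)/60 = 30,646; divided by 519,180.5, this is 5.9%.

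*Effect on the cohort.* Let r be the relative excess above. For deaths from day 0, late entrants are mr/(1 + mr) of the cohort, and the 90-day death proportion becomes m(1 + r)/(1 + mr). For deaths from day 30, replace m by m × 60/90.

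| Case | Late entrants, share of cohort | 90-day death proportion |
|---|---|---|
| m = 1%, flat, second prescription at day 30 | 0.02% | 0.67% → 0.69% |
| m = 3%, flat, second prescription at once | 0.13% | 3.00% → 3.13% |
| m = 3%, linear, second prescription at once | 0.27% | 3.00% → 3.26% |
| m = 5%, linear, second prescription at once | 0.45% | 5.00% → 5.43% |

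Per 1,000 men with valid index dates and m = 3%, the 30 early deaths become about 31.3 (flat) or 32.7 (linear).

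**The case against.** The strongest reply is that the effect is too small to matter in a descriptive study with exploratory comparisons. Much of that stands. The late entrants are a fraction of a percent of the cohort, and the limitations section describes entrants as having returned for a second month of treatment, which favours the lower end of the range (3–6% more early deaths). PDC is largely protected, because section 9.7.3 requires complete follow-up over each fixed period. The identification period is worded for relugolix use rather than for index dates, so the plan does not promise to accept every start up to the last day, and a start on that day could hardly qualify without a second prescription.

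Several stronger readings are also tempting, and the documents do not support them:
- *That the fourth quarter of 2023 would be made up only of men who died.* Starters on 1 and 2 October can qualify alive, and Table 2 classifies index date by calendar year, so late entrants are pooled with all other 2023 starters.
- *That these men have no survivors beside them in the persistence curve.* That is true by calendar date only. Kaplan-Meier time runs from the index date, so they are at risk alongside the whole cohort.
- *That the race comparison is biased.* Nothing in the plan shows that the late decedents would differ by race.
- *That the primary baseline table is materially distorted toward sicker men.* Greater illness is a reasonable guess, but at under 0.5% of the cohort they can hardly move a percentage.

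The sample-selection figure is not visible in the text reviewed, so an index cutoff stated there cannot be ruled out. None of this removes the mechanism: no visible text prevents entry by death alone from the last 90 days.

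**Conclusion.** The selection on outcome follows from the written dates and criteria and needs no assumption beyond how the index day is counted. Its direction is certain: it can only add early deaths, and hence early non-persistence. Its size rests on assumed uptake, assumed 90-day mortality of 1–5% and assumed timing of the second prescription. Under these it is about 3–9% more 90-day deaths in relative terms, at most about 0.4 percentage points on the 90-day death proportion, and under 0.5% of the cohort. It would not overturn a result, but it is a definable flaw in cohort entry that is not disclosed and is nearly free to remove, so it should be corrected before the cohort is drawn.

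**What to change.** In the abstract and section 9.1, and by adding it to the index-date definition in section 9.2.1 (which now carries no identification date), state that the index date, meaning the first relugolix prescription, must fall from 18 December 2020 to 2 October 2023, that is, no later than data end minus 90 days. State whether the index day is day 0 or day 1; if day 1, the last date is 3 October.

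Apply the cutoff to the index date only. Second prescriptions, deaths and follow-up should still count through 31 December 2023. Closing the whole prescription window on 2 October could drop September starters whose second prescription came later.

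The death exception then covers only men who could have been followed for 90 days. Capping the index date is preferable to admitting late survivors with censoring, because the 90 days after index also define the index regimen, metastatic status and the trial-participation exclusion, which would be incomplete for those men.

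The cost is a few sentences of text and a few late-2023 decedents. No eligible survivor is lost, provided the cutoff matches the day-counting convention.
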